11.4.3 Exploratory comparisons

Exploratory analysis I is analogous to primary analysis I and secondary analysis I except that the analysis cohort will be the full M6 cohort (FM6). The same stratification and covariate adjustment strategies used in secondary analysis I will be adopted here.

Exploratory analysis II is analogous to the secondary analysis III except that the analysis cohort will be the FM6 PLWH/PLWoH. The same stratification and covariate adjustment strategies used in secondary analysis III will be adopted here.

Exploratory analysis III seeks to compare the COVID-19 incidence among participants in Analysis Group 1 vs. Analysis Group 2-1 (defined at baseline/enrollment) counting events from enrollment. To this end, the following Cox regression model is considered:

$$\lambda_{ji}(t | A_i, W_i) = \lambda_{0j}(t) \exp \{ \beta A_i + \beta_1 Z_i(t) + \beta_2 A_i Z_i(t) + \gamma^T W_i \} I(t > \tau_i^{\text{enroll}}), \quad (6)$$

with $A_i = 1$ if participant i is in AG 2-1 and 0 if in AG 1, and $Z_i(t)$ is a time-varying indicator of receiving a M6 booster vaccine. The analysis will consider the same stratification and covariate adjustment strategy as specified in the pre-M6 SAP. Key parameters of interest include $\exp\{\beta\}$, $\exp\{\beta_1\}$ and $\exp\{\beta_2\}$.

Exploratory analysis IV and V are analogous to exploratory analysis III and will adopt the same stratification and covariate adjustment strategies.

Exploratory analysis VI and VII are analogous to the hybrid vs. vaccine-induced comparison as specified in the pre-M6 SAP, except that the analysis will define the hybrid vs. vaccine immunity status based on M6 and count events 13 days post M6 vaccination. The analyses will adopt the same stratification and covariate adjustment strategies as its pre-M6 counterpart.

12 Multiplicity adjustment

For all analyses, point estimates, 95% CIs and nominal p-values will be displayed in forest plots without multiplicity adjustment. No multiple hypothesis testing will be done in any described analyses.

13 Handling missing data

A small number (about 5%) of PLWH participants are missing CD4 cell count and/or HIV-1 viral load at enrollment or at Month 6. In order to adjust for CD4 cell count and HIV VL in various analyses and retain these participants, hard-imputation is used to assign a fixed CD4 cell count value and VL value for each of the participants with missing data. Specifically, for baseline values, within each study group (Group 1 or 2), HIV anti-retroviral therapy (ART) status (Yes, No or Missing) and Sex (Female or Male), missing baseline CD4 cell count is imputed to be the median CD4 count of those with observed baseline data. The same imputation is done for missing baseline VL. For Month 6 values, missing data will be imputed as the baseline observed or imputed value for CD4 cell count and VL. Missing data of history of TB at Month 6 is defined as negative.

References

Grambsch, P. M. and Therneau, T. M. (1994), “Proportional hazards tests and diagnostics based on weighted residuals,” *Biometrika*, 81, 515–526.

Approved

Signature Page for SCHARP-TMF-118029 v2.0

Reason for signing: Approved	Name: [name] Role: I am an author of the document. Date of signature: 01-Apr-2024 19:29:49 GMT+0000
Reason for signing: Approved	Name: [name] Role: I am an author of the document. Date of signature: 01-Apr-2024 19:56:27 GMT+0000
Reason for signing: Approved	Name: [name] Role: I reviewed and approved the document and am signing in lieu of or on behalf of another individual. Date of signature: 01-Apr-2024 21:23:53 GMT+0000
Reason for signing: Approved	Name: [name] Role: I am an author of the document. Date of signature: 02-Apr-2024 00:55:44 GMT+0000

Signature Page for SCHARP-TMF-118029 v2.0

Approved

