**Table 2-1 Vaccine efficacy and effectiveness for the ancestral strain of SARS-CoV-2 and Variants of Concern**

Manufacturer	Vaccine	Vaccine efficacy against ancestral strain for symptomatic infection (severe COVID-19)	Vaccine Effectiveness for VOC against Symptomatic Infection (Severe COVID-19) (27)			
			Alpha (B.1.1.7)	Beta / Gamma (B.1.351 / P.1)	Delta (B.1.617.2)	Omicron (B.1.1.529) 
Moderna	mRNA-1273	94 (100)% (8)	91 (94)%	78 (94)%	70 (96)%	75.1 (75-85 against hospitalization)%
Pfizer	BNT162b2	95(100)% (13)	90 (95)%	85 (98)%	85 (95)%	65.5 (80 against hospitalization)%
Johnson and Johnson (JNJ)	Ad26.COV 2.S	66 (85.4)% (28, 29)	N/A (N/A)	52 (65-66 against hospitalization; 91-95 against mortality)%	N/A (71)%	N/A (N/A)
Novavax	NVX-CoV2373	89.7 (100)% (26)	86%	60%	60%	N/A (N/A)
AstraZeneca	AZD1222 (ChAdOx1)	67 (100)% (30)	80 (95)%	Under 70% (N/A)	70 (95)%	48.9 (70 against hospitalization)%

Note: refer to Tregoning et al., 2021 (31) and Cevik et al, 2021 (27) for a review of the COVID-19 vaccine effort, SARS-CoV-2 variants versus efficacy, effectiveness, and escape.

 Effectiveness at week 4 post 2nd dose; effectiveness dropped in the following weeks (32, 33).

While the currently approved mRNA vaccines have demonstrated durable efficacy against severe COVID-19 disease (34, 35), high rates of breakthrough and repeat infections have highlighted their reduced efficacy against infections from new variants of concern (VOCs) (see Table 2-1), particularly Omicron (B.1.1.529 [BA.1]) and its lineages (eg, BA.2, BA.2.12.1, BA.3, BA.4, BA.5). There is therefore a strong interest in developing updated vaccines to provide broader protection against current and future VOCs. To that end, Moderna, along with Pfizer-BioNTech, has developed new bivalent versions of its mRNA vaccine that include equal parts of mRNA encoding the S protein of the ancestral SARS-CoV-2 (eg, mRNA-1273) as well as mRNA encoding for that of a VOC. Preliminary studies of such bivalent vaccines have been highly encouraging. The vaccine candidate mRNA-1273.211 (mRNA-1273 plus mRNA encoding the S protein of Beta) elicited significantly higher neutralizing antibody responses to the ancestral strain as well as variants (eg, Beta, Delta, and Omicron) compared to mRNA-1273

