For this exploratory analysis of COVID-19 and severe COVID-19 between baseline hybrid vs. vaccine immunity groups using the first definition described above, the same analysis will be repeated for three subsets of participants: 1) participants who received the monovalent Month 6 booster; 2) participants who received the bivalent Month 6 booster; and 3) participants who did not receive the Month 6 vaccination. An analysis will be performed only if there are at least 7 endpoints in a given subset of participants. These analyses seek to understand if participants' COVID-19 and severe COVID-19 risk differs between baseline hybrid and vaccine immunity groups, counting events starting 1 day after enrollment till Month 12 or Month 18 (as opposed to Month 6 in the Part A analyses). All covariates considered in the Part A analyses of hybrid vs. vaccine immunity will be considered. In addition, Month 6 vaccination will be included as a time-varying covariate using the Cox model approach. The cumulative incidence approach will not be considered for these exploratory analyses.

Comparing Month 6 hybrid vs. vaccine immunity groups among PLWH

For this exploratory analysis of COVID-19 and severe COVID-19 between Month 6 hybrid vs. vaccine immunity groups based on the 2nd definition described above, the same analysis will be repeated for two subsets of participants: 1) participants who received the monovalent Month 6 booster; and, 2) participants who received the bivalent Month 6 booster. An analysis will be performed only if there are at least 7 endpoints in a given subset of participants. These analyses seek to understand if participants' COVID-19 and severe COVID-19 risk after the Month 6 vaccination differs between hybrid and vaccine immunity groups defined at Month 6, counting events starting 14 days after the Month 6 vaccination date. All covariates considered in the Part A analyses of hybrid vs. vaccine immunity will be considered, except that the covariate values are defined at Month 6 whenever applicable. Only the Cox model approach will be considered for these analyses; the cumulative incidence approach will not be considered.

9 Summary of primary, secondary and exploratory analyses

Table 2 summarizes the target population, study endpoints, and time frame for various primary and secondary analyses. Table 3 further summarizes the same information for various exploratory

analyses.

	Primary analysis I (applicable when # COVID-19 endpoints is at least 20)

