10.1 Cumulative-failure-time-based parameters of interest

Let T be the failure time using the study time scale (based on one of the study time origins defined above), t_0 a fixed time point of interest after the given time origin, and W baseline covariates. For a given analysis, we denote by A a binary indicator of belonging to either of strata which define the comparison groups of interest. In the primary analysis A is indicator of receiving a bivalent or monovalent M6 booster (in analyses), and it is similarly defined elsewhere. We denote by $T(a)$ the counterfactual failure time if $A = a$.

In a cumulative-incidence-based analysis, parameters of interest are the marginalized failure time

Comparing bivalent vs. monovalent booster		
Exploratory analysis I		
Target population	FAS participants receiving a M6 vaccine regardless of randomization scheme (FM6)	
Endpoint	COVE-/CDC-based/Severe (when applicable) COVID-19 endpoints counted 1 day after M6 vaccination	
Time frame	M6 vaccination to M12/M18 visit	
Exploratory analysis II		
Target population	FAS PLWH/PLWoH receiving a M6 vaccine regardless of randomization scheme (FM6)	
Endpoint	COVE-/CDC-based/Severe (when applicable) COVID-19 endpoints counted 1 day after M6 vaccination	
Time frame	M6 vaccination to M12/M18 visit	
Comparing baseline hybrid vs. vaccine immunity among PLWH		
Exploratory analysis III		
Target population	AG1 and AG2.1 receiving a bivalent M6 vaccine regardless of randomization scheme (AG1 and AG2.1 in FM6)	
Endpoint	COVE-/CDC-based/Severe (when applicable) COVID-19 endpoints counted 1 day after enrollment	
Time frame	Enrollment to M12/M18 visit	
Exploratory analysis IV		
Target population	AG1 and AG2.1 receiving a monovalent M6 vaccine regardless of randomization scheme (AG1 and AG2.1 in FM6)	
Endpoint	COVE-/CDC-based/Severe (when applicable) COVID-19 endpoints counted 1 day after enrollment	
Time frame	Enrollment to M12/M18 visit	
Exploratory analysis V		
Target population	AG1 and AG2.1 not receiving M6 vaccination regardless of randomization scheme (AG1 and AG2.1 in FM6)	
Endpoint	COVE-/CDC-based/Severe (when applicable) COVID-19 endpoints counted 1 day after enrollment	
Time frame	Enrollment to M12/M18 visit	
Comparing Month 6 hybrid vs. vaccine immunity among PLWH		
Exploratory analysis VI		
Target population	AG1 and AG2.1 receiving a monovalent M6 vaccine regardless of randomization scheme (AG1 and AG2.1 in FM6)	

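### In exploratory analyses III and IV, exp(β1) is listed as a key parameter but cannot be separated from time since enrolment, and the post-dose hybrid vs vaccine contrast exp(β+β2) is not listed

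*SAP*

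**What the plan says.** SAP 8.2.2 plans a comparison of baseline hybrid immunity (AG2.1, one dose before Month 6) with baseline vaccine immunity (AG1, two doses) among PLWH, "counting events starting 1 day after enrollment till Month 12 or Month 18 (as opposed to Month 6 in the Part A analyses"). It adds: "In addition, Month 6 vaccination will be included as a time-varying covariate using the Cox model approach".

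SAP 11.4.3 turns this into model (6):

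λ_j(t) = λ_0j(t) · exp{βA + β1 Z(t) + β2 A·Z(t) + γ'W}, for t after enrolment,

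where A = 1 for AG2.1 and 0 for AG1, and Z(t) "is a time-varying indicator of receiving a M6 booster vaccine". SAP 10.3 sets t on the calendar scale. After "Key parameters of interest include" the SAP lists exp(β), exp(β1) and exp(β2). On W and the strata it says: "The analysis will consider the same stratification and covariate adjustment strategy as specified in the pre-M6 SAP".

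SAP Table 3 gives the population of analysis III as "AG1 and AG2.1 receiving a bivalent M6 vaccine regardless of randomization scheme (AG1 and AG2.1 in FM6") and of analysis IV as "AG1 and AG2.1 receiving a monovalent M6 vaccine regardless of randomization scheme (AG1 and AG2.1 in FM6"). People without a Month 6 dose are analysed separately, in analysis V. Protocol Appendix K places the Month 6 dose at Day 169 with an allowable window of −28/+28 days.

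**The concern.** A calendar-time baseline absorbs the course of the epidemic. It does not absorb how risk changes with time since a person's own enrolment. In III and IV everyone is dosed at about the same interval after enrolment, and nobody stays undosed. On any calendar date, the people with Z = 1 enrolled roughly six months or more earlier and those with Z = 0 enrolled more recently. Anything that changes risk over that interval enters β1 together with any effect of the dose.

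Two such patterns are plausible here, and they act in opposite directions. The footnote to Protocol Table 2-1 says of Omicron that "effectiveness dropped in the following weeks". Such waning would raise exp(β1) and so count against the booster. Counting also starts 1 day after enrolment, when AG1 has had only the first of its two doses. Excess risk in that early period would lower exp(β1).

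The second part needs no assumption. With A·Z(t) in the model, exp(β) is the hybrid vs vaccine hazard ratio before the Month 6 dose only, which is the Part A question. After the dose the ratio is exp(β+β2). That is what extending follow-up beyond Month 6 adds, and it is not among the listed parameters. A reader of the planned output would get a coefficient that is hard to interpret and would lack the contrast the analysis was extended to provide.

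**Working it through.** The documents give no sample size, event count or power for these analyses, so there is no plan figure to reproduce.

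**Inputs from the documents**
- Dose window: 169 − 28 = Day 141 to 169 + 28 = Day 197.
- Interim incidence in PLWH (Protocol 2.1): 7.1%/yr vaccine-only and 2.2%/yr hybrid; 2.2/7.1 = 0.31.
- Enrolment spread: 27 months total (Protocol 1) less 18 months per participant leaves about 9 months, or 39 weeks. About 4,000 of 14,237 were dosed under version 6 (Protocol 6.3.1, SAP 2): 4,000/14,237 = 28%, and 0.28 × 39 ≈ 11 weeks if accrual was even.

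**Assumptions, because the documents give no figure**
- Hazard is flat to week 6 after enrolment, then multiplied by w per 20 weeks until week 26 or week 52. With w = 2 the total rise is 2-fold by week 26, or 2^(46/20) ≈ 4.9-fold by week 52.
- Most doses fall in the target window. Enrolment is spread over 11, 26 or 39 weeks and follow-up is 52 or 78 weeks.
- The early-excess case doubles the AG1 hazard for the first 6 weeks, with no waning.
- W holds no enrolment-date term.

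**Collinearity.** Under these settings, Z(t) equals the indicator of at least 24 weeks since enrolment in 97% of person-weeks.

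**What model (6) estimates.** The large-sample values solve the expected partial-likelihood score on a weekly calendar grid:

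Σ_t Σ_i d_i(t) · [x_i(t) − x̄(t; b)] = 0,

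with x = (A, Z, A·Z), d_i(t) the expected events, and x̄ the mean of x over the risk set weighted by exp(b'x). With a true booster hazard ratio of 1.0:

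| Time pattern | exp(β1) | exp(β2) | exp(β+β2) |
|---|---|---|---|
| None | 1.00 | 1.00 | 0.31 |
| w = 1.5 in both groups | 1.07–1.44 | 1.00 | 0.31 |
| w = 2 in both groups | 1.13–1.88 | 1.00 | 0.31 |
| w = 2 in AG1 only | 1.24–2.07 | 0.32–0.65 | see below |
| Early AG1 excess, no waning | 0.87–0.92 | 1.25 | 0.25 × 1.25 = 0.31 |

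The w = 2 row splits into 1.13–1.18 with 11-week enrolment and 1.41–1.88 with 39-week enrolment. A separate solution of the same kind gave 0.86 for early excess.

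The same mixing affects a useful booster. A true hazard ratio of 0.6, with w = 2 in both groups to week 52, reads as 0.71 (11-week enrolment) or 1.11 (39-week).

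**Why exp(β+β2) holds up.** It compares the two groups after the dose, so a time course they share cancels. In the AG1-only case (rise to week 52, 39-week enrolment, 52-week follow-up) the fit gives 0.24 × 0.41 ≈ 0.10. That differs from 0.31 because the post-dose hazards really do differ in that scenario, so it is still the contrast asked for.

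**The case against.** The strongest reply is that the SAP does not plan the misreading. Its stated aim is the hybrid vs vaccine comparison. Month 6 vaccination enters as a time-varying covariate, and nowhere is exp(β1) or exp(β2) called a booster effect. SAP 11.2 states one Cox null hypothesis, β = 0, so false-positive rates computed for β1 or β2 would concern tests the SAP does not name. This stands. What remains is that the coefficient of a booster indicator is listed as key with no statement of what it means.

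A reader might infer that an inert booster will look harmful and a useful one inert. The documents do not support that as a general statement, because the direction depends on which time pattern dominates. With enrolment over 9 months and a linear rise to Month 6 followed by a plateau, shared 1.5-fold waning combined with doubled early AG1 hazard gives exp(β1) of 1.00, and 2-fold gives 1.09.

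W is unseen. If the pre-Month 6 SAP adjusts for enrolment date, that acts as a linear time-since-enrolment term on the calendar scale and would remove part of the problem. Nothing available says that it does.

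It is also fair that exp(β2) is simply exp(β+β2)/exp(β), that the key list is worded as inclusive rather than exhaustive, and that analyses VI and VII already compare hybrid with vaccine immunity after Month 6. However, VI and VII redefine the groups at Month 6, so they do not give the post-dose contrast for the baseline groups. SAP 11.4 plans Schoenfeld-residual checks, but these examine proportionality over calendar time and do not target this problem.

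**Conclusion.** The point holds as an interpretive defect in two exploratory analyses. In III and IV, exp(β1) cannot be separated from time since enrolment, and the post-dose contrast that SAP 8.2.2 calls for is not listed. Both follow from the model and the populations in Table 3, subject to the unseen W.

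The size and sign of the distortion are not established. For an inert booster, exp(β1) is about 1.07 to 1.9 under assumed shared waning of 1.5- to 2-fold per 20 weeks, depending on enrolment spread and on when the rise stops. It is about 0.86 to 0.92 under assumed early excess without waning. exp(β2) stays at 1.00 when the time course is shared and moves only when AG1 and AG2.1 differ.

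It would go too far to say that the SAP plans to claim a booster effect here, or that the booster will be made to look worse. The consequence is limited: SAP 8.2 says the exploratory analyses may not all be performed for the primary publication, and the primary and secondary comparisons of randomised arms do not use model (6).

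**What to change.** In SAP 11.4.3, for analyses III and IV:
- Name exp(β) (hybrid vs vaccine before the Month 6 dose) and exp(β+β2) (after it) as the key parameters, each with a 95% CI.
- Drop exp(β1) from the key parameters.
- If exp(β2) is kept, label it as the change in the hybrid vs vaccine hazard ratio from before to after the dose.
- State that neither exp(β1) nor exp(β2) estimates a booster effect.
- State whether W includes enrolment date.

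The cost is SAP wording and one linear combination of fitted coefficients. No new data are needed, and the downside is one fewer headline parameter.

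A joint model that brings in never-boosted participants and a flexible time-since-enrolment term by group is optional. For an inert booster with 2-fold waning per 20 weeks in both groups to week 52 and 39-week enrolment, adding an assumed 15% never-boosted participants and a piecewise term returned exp(β1) to 1.00, with a standard error of 0.32 for an assumed 533 AG1 and 1,067 AG2.1 participants. The same controls without the time term left it at 1.42, so both parts are needed. The model relies on non-randomised non-recipients, so its result would stay exploratory.
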